9.4. Data sources

Subjects will attend the investigator site for regular visits during their treatment with Polyoxidonium according to local clinical practice. Data collection will be based on the review of medical records and routine examination of subjects. Regular medical records at study sites will serve as data sources. Relevant data will be entered into study database via eCRF by site personnel.

9.5. Study size

Due to the explorative character of the study and absence of the hypothesis to test, no formal attempt to calculate the sample size and power has been made.

A total of 500 subjects are expected to enter the study. It is assumed, that this number of subjects will allow to characterize the safety profile of Polyoxidonium and will be sufficient to identify, quantify and describe statistically the frequency of at least common ($\geq 1/100$, $< 1/10$) and uncommon ($\geq 1/1000$, $< 1/100$) adverse events and to allow for various subgroup analyses.

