9. RESEARCH METHODS

9.1. Study design

This PASS is a local, multicentre, prospective, open-label, non-interventional, uncontrolled study.

Patients for whom Polyoxidonium is prescribed as a part of routine clinical practice will be eligible for this study. The decision to prescribe Polyoxidonium will be independent of the decision to enroll the subject into the study.

Primary treatment of a disease, Polyoxidonium administration, diagnostic procedures and assessments as well as visits schedule will be left at the discretion of investigators, according to local guidelines and routine clinical practices.

The study is explorative in nature. It is undertaken to systematically collect safety information in a community-based sample of subjects receiving Polyoxidonium therapy in routine care setting, to quantify potential risks, investigate potential risk factors and effect modifiers, or to provide evidence about the absence of risks.

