9.7.1. Statistical methods

This study focuses primarily on the safety profile of Polyoxidonium and no statistical hypothesis testing is intended. Statistical analysis will be merely descriptive in nature.

Categorical data will be summarized in frequency tables. For continuous data, descriptive statistics (mean, median, minimum, maximum, standard deviation, 5% percentile, and 95% percentile) will be calculated. Comparative statistical analysis will be also performed. For statistical comparison of categorical data, the chi-square test will be used. Parametric Student t-test or nonparametric Wilcoxon rank sum test will be used for comparison of continuous data between two independent samples. Parametric paired Student t-test or nonparametric Wilcoxon signed-rank test will be used for comparison of continuous data between two dependent samples. Proportions of two dependent samples will be compared using McNemar's test. Statistical tests will be interpreted at the 5% significance level (two-sided).

A stratified analysis of main event of interest (i.e., adverse renal effect) will be performed by prior renal impairment and by use of concomitant nephrotoxic medicines to control confounders. Logistic regression will be employed to determine factors as possible predictors of adverse renal effects.

Stratified analysis by indication will be performed to investigate safety profile and clinical benefit in different subjects subgroups.

Data will be analyzed using SPSS software.

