9.7.2. Safety evaluation

All subjects who receive at least one dose of Polyoxidonium will be subjected to the safety analysis.

Safety endpoints will be analysed per infusion and per subject at each individual study visit.

Safety endpoints are listed in Section 9.3.2.

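### Section 9.5 says 500 subjects suffice to identify and quantify adverse events as rare as 1/1000, but at that rate the study would more likely than not see no case

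*Protocol*

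**What the plan says.** Section 9.5 explains that, because the study is exploratory and tests no hypothesis, "no formal attempt to calculate the sample size and power has been made". It continues: "A total of 500 subjects are expected to enter the study". It then assumes that this number "will be sufficient to identify, quantify and describe statistically the frequency of at least common" and uncommon events, printing the uncommon class as at least 1/1000 and below 1/100. The same sentence adds that the number will suffice to describe these "adverse events and to allow for various subgroup analyses".

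Section 9.1 lists the purposes of the study: quantifying potential risks, looking at risk factors and effect modifiers, "or to provide evidence about the absence of risks". Under section 8, both parts of the primary objective are frequencies (adverse drug reactions, and the proportion with adverse renal effects), and the study belongs to a Risk Management Plan. The limitations in section 9.9 do not mention study size.

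**The concern.** Section 9.5 gives numerical limits for the event rates it claims to cover, so the claim can be tested even though no calculation stands behind it. A cohort of 500 expects half a case of an event with a true rate of 1/1000, which cannot support a claim to find such events, still less to estimate their frequency.

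What is at stake is the reading of a null or near-null result. Section 7.2 reports no organ-specific adverse effects from clinical development or routine pharmacovigilance, so zero or very few renal cases is a realistic outcome. Read with sections 9.1 and 9.5, zero cases would appear to cover rates down to 1/1000 and to speak for the absence of renal risk, while rates several times higher remain compatible with the data. The uncommon class also matters for the adverse drug reaction objective: section 4.8 of the product characteristics (Annex 4) places skin redness and induration there.

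**Working it through.** **Inputs**

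- Planned size: N = 500, one uncontrolled cohort (section 9.5).
- Safety denominator: "All subjects who receive at least one dose of Polyoxidonium will be subjected to the safety analysis" (section 9.7.2), so at most 500 if 500 enter.
- Classes: uncommon 0.1% to below 1%; common 1% to below 10% (section 9.5).
- Confidence level: 95%, two-sided, matching the 5% two-sided level in section 9.7.1. One-sided limits are also shown.
- Detection target: none is stated, so 80%, 90% and 95% are shown as an assumed range.
- Ascertainment: every case is assumed to be recorded, which is the best case.

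The protocol gives no formula, detection probability or precision target, so 500 cannot be reproduced as a calculated figure. The sufficiency statement is tested directly.

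**Step 1. Chance of seeing a case.** P(at least 1) = 1 − (1 − p)^500. At p = 0.001 this is 1 − 0.999^500 = 1 − 0.606 = 0.394. The other columns are binomial tails with n = 500.

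| True rate | Expected cases | P(≥1) | P(≥2) | P(≥3) |
|---|---|---|---|---|
| 0.1% | 0.5 | 39.4% | 9.0% | 1.4% |
| 0.2% | 1.0 | 63.2% | 26.4% | 8.0% |
| 0.3% | 1.5 | 77.7% | 44.2% | 19.1% |
| 0.5% | 2.5 | 91.8% | 71.4% | 45.7% |
| 0.6% | 3.0 | 95.1% | 80.2% | 57.8% |
| 1.0% | 5.0 | 99.3% | 96.0% | 87.7% |

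**Step 2. Lowest rate detectable with 500, and N needed at 1/1000.** For detection probability D, the lowest rate is p = 1 − (1 − D)^(1/500), and the size needed is N = ln(1 − D)/ln(0.999), rounded up.

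| D | Lowest rate with N = 500 | N needed at 0.1% |
|---|---|---|
| 80% | 0.32% | 1,609 |
| 90% | 0.46% | 2,302 |
| 95% | 0.60% | 2,995 |

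For the 95% row: 1 − 0.05^(1/500) = 0.00597, and ln(0.05)/ln(0.999) = 2,994.2.

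The part of the uncommon class that falls short of 95% detection is (0.597 − 0.1)/0.9 = 55% on the linear scale and log10(0.597/0.1) = 78% on the log scale. For 80% detection the shares are 25% and 51%.

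**Step 3. Precision.** Exact (Clopper-Pearson) 95% limits:

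| Cases in 500 | Estimate | 95% limits |
|---|---|---|
| 0 | 0% | 0 to 0.74% |
| 1 | 0.2% | 0.005% to 1.11% |
| 2 | 0.4% | 0.05% to 1.44% |
| 3 | 0.6% | 0.12% to 1.74% |
| 4 | 0.8% | 0.22% to 2.04% |
| 5 | 1.0% | 0.33% to 2.32% |
| 25 | 5.0% | 3.26% to 7.29% |

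For zero cases the two-sided upper limit is 1 − 0.025^(1/500) = 0.74% and the one-sided limit is 1 − 0.05^(1/500) = 0.60%. Every count from 1 to 4 has a point estimate in the uncommon class and an upper limit in the common class. The last row shows that a common event is estimated usefully.

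**Step 4. Subgroups.** Section 9.2.1 lists five indications. An even split, which is an assumption, gives 500/5 = 100 per subgroup. Then P(at least 1) is 1 − 0.99^100 = 63% at a rate of 1% and 1 − 0.999^100 = 9.5% at 0.1%. Zero cases in 100 leaves a two-sided upper limit of 3.6%.

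**Step 5. Fewer evaluable subjects.** With 450 or 400 evaluable (assumptions), P(at least 1) at 0.1% falls to 36% or 33%.

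**The case against.** The strongest reply is that section 9.5 is candid: it says no calculation was made, gives the reason, and presents the sufficiency statement as an assumption. Section 9.7.1 calls the analysis descriptive, and no decision rule depends on the sentence. This explains why there is no power calculation. It does not make the assumption correct.

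A second reply is that the protocol sets no detection target, so how much of the class fails depends on the threshold chosen. That is fair. One case becomes more likely than not from about 0.14%, and at 80% detection about three quarters of the class on the linear scale is covered. But at the 1/1000 bound that section 9.5 itself names, the chance is 39%, below any reasonable threshold. Likewise no precision target is set, so 5/500 with its wide interval is still a description of frequency. An interval that cannot place the event in its class is nevertheless poor quantification.

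Third, the over-reading of a null result is an inference, because the protocol sets no rule for interpreting zero cases. That stands, although the aim in section 9.1 invites that reading.

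Fourth, section 9.7 allows analyses to be dropped when data are sparse. This limits the subgroup problem in practice but leaves the assurance in section 9.5 uncorrected.

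Finally, the figures above assume complete ascertainment, while laboratory tests are recorded only where routine care produces them (Table 1, section 9.2.5) and the renal event in section 9.3.1 leans on such tests. This point makes matters worse for the claim. If half of true cases were recorded (an assumption), the chance of seeing one at a true rate of 0.6% would be 1 − 0.997^500 = 78%. Any replacement wording should therefore speak of recorded cases.

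**Conclusion.** The concern holds. Five hundred subjects do not suffice to find or quantify events across the uncommon class as section 9.5 defines it. At its lower bound the study has a 60.6% chance of seeing no case. Detection reaches 80% at 0.32% and 95% at 0.60%, about three and six times that bound. Zero cases leaves rates up to 0.74% (two-sided) or 0.60% (one-sided) unexcluded.

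The failure is not total: from about 0.6% upward at least one case is very likely, and common events are well supported. The results rest on independent subjects, 500 treated and every case recorded; loss of subjects or incomplete recording would weaken them further. The subgroup figures also rest on the assumed size of 100. Because the statement is made in the protocol itself and bears on both primary objectives, it should be corrected there.

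**What to change.** Keep N at 500 and restate section 9.5 along these lines:

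> *With 500 treated subjects there is a 95% probability of at least one recorded case of an event whose recorded incidence is 0.6% or more (80% at 0.32%; 39% at 0.1%). If no case is recorded, the two-sided exact 95% upper limit is 0.74%. Common events can be quantified. Events in the lower part of the uncommon range may be missed. Subgroup results are descriptive.*

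In section 9.1, replace the absence-of-risk aim with an upper confidence limit for the risk. Since section 9.7.1 lists no confidence intervals, name the exact binomial interval there or in the SAP. Add the size limitation to section 9.9.

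The cost is wording and one standard interval, with no extra subjects or procedures. The stated capability becomes less favourable. If the sponsor does want coverage down to 1/1000, about 1,600 subjects (80% detection) to 3,000 (95%) would be needed instead.

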9.6. Data management

A Data Management (DM) vendor will be responsible for eCRF development and data management of this study, including data quality checking.

All required data for this study will be collected on the eCRF using the QCTMS EDC™ system. An appropriate internet access is required for data entry.

Sites will receive training and have access to a manual for appropriate eCRF completion. All eCRFs should be completed by authorized trained site staff, who will transcribe the collected subject data from paper source documents into the eCRF. eCRFs should be reviewed and electronically signed by the investigator.

For classification purposes, preferred terms will be assigned to the original terms entered on the eCRF, using the current version of the Medical Dictionary for Regulatory Activities (MedDRA) terminology for adverse events and the International Non-proprietary Names (INN) for concomitant medicines.

An audit trail will maintain a record of initial entries and changes made, reasons for change, time and date of entry, and user name of person authorizing entry or change. The data will be transferred directly to the clinical database.

At the end of the study, the investigator will receive subject data for his/her site in a readable format on a compact disc that must be kept with the study records. Acknowledgement of receipt of the compact disc will be required.

eCRFs are confidential documents and will only be available to Sponsor (including Sponsor vendors), the investigator and Regulatory Authorities.

9.7. Data analysis

This section provides specifications for preparation of Statistical Analysis Plan (SAP), which will be issued prior to database lock. The statistical analysis will be performed according to the nature of considered data. If the data situation does not allow for an adequate presentation of an envisaged parameter or stratification e.g. due to sparse data, the respective analysis will not be performed. Any differences compared to this statistical section should be identified and documented in final SAP.

Statistical analyses will be made after the approval of the SAP and the database lock.

9.7.1. Statistical methods

This study focuses primarily on the safety profile of Polyoxidonium and no statistical hypothesis testing is intended. Statistical analysis will be merely descriptive in nature.

Categorical data will be summarized in frequency tables. For continuous data, descriptive statistics (mean, median, minimum, maximum, standard deviation, 5% percentile, and 95% percentile) will be calculated. Comparative statistical analysis will be also performed. For statistical comparison of categorical data, the chi-square test will be used. Parametric Student t-test or nonparametric Wilcoxon rank sum test will be used for comparison of continuous data between two independent samples. Parametric paired Student t-test or nonparametric Wilcoxon signed-rank test will be used for comparison of continuous data between two dependent samples. Proportions of two dependent samples will be compared using McNemar's test. Statistical tests will be interpreted at the 5% significance level (two-sided).

A stratified analysis of main event of interest (i.e., adverse renal effect) will be performed by prior renal impairment and by use of concomitant nephrotoxic medicines to control confounders. Logistic regression will be employed to determine factors as possible predictors of adverse renal effects.

Stratified analysis by indication will be performed to investigate safety profile and clinical benefit in different subjects subgroups.

Data will be analyzed using SPSS software.

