9.3.2. Safety variables

Safety variables include:

- proportion of subjects with adverse renal effects (as defined in Section 9.3.1)
- proportion of subjects, who experienced any AE;
- proportion of subjects with ADRs;
- proportion of subjects experiencing serious adverse events (SAEs);
- proportion of subjects with serious ADRs;
- severity of AEs;

- number of subjects who discontinued the study and the reasons for drop-outs;
- global assessment of tolerability by investigators: very good (no intolerance reactions), good (occasional intolerance reactions), moderate (frequent intolerance reactions), poor (intolerance reactions after every use);
- global assessment of tolerability by subjects: very good, good, moderate and poor.

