9.3.3. Clinical benefit variables

Clinical benefit assessment includes the following variables:

- global assessment of improvement by subjects score (0 to 4 scale: 0=much worse; 1= somewhat worse; 2=same; 3=somewhat improved; 4 = greatly improved)
- global assessment of improvement by investigators score (0 to 5 scale: 0 = worse; 1 = no appreciable improvement; 2 = slight improvement; 3 = moderate improvement; 4 = marked improvement; 5 = complete resolution)
- mean duration of primary treatment of disease (i.e., days with antibiotic use in case of infection or antiallergic medication in case of allergies),
- days with fever $>38^{\circ}\text{C}$ /days with symptoms,
- total and differential WBC count in blood and urine (if data are available).

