11.2.1 Assessment of severity of adverse event

Severity of adverse events should be graded as follows:

- Mild – usually transient in nature and generally not interfering with patient’s normal activities;
- Moderate – sufficiently discomforting to interfere with patient’s normal activities;
- Severe – prevents patient’s normal activities.

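### Section 9.7.1 names only the chi-square test for comparing independent groups on categorical data, so the ordered tolerability grades would be tested as if they had no order

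*Protocol*

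**What the plan says.** Protocol section 9.7.1 sorts its tests by type of data.

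- Categorical data: "For statistical comparison of categorical data, the chi-square test will be used".
- Continuous data: "Parametric Student t-test or nonparametric Wilcoxon rank sum test will be used for comparison of continuous data between two independent samples". Paired continuous data get the corresponding paired tests.
- Paired proportions: "Proportions of two dependent samples will be compared using McNemar's test".
- Possible predictors of the renal event: logistic regression.

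The tests are read at a two-sided 5% level. Ordered categories are not mentioned, and no trend or ordinal test is named. The section also plans subgroup work: "Stratified analysis by indication will be performed to investigate safety profile and clinical benefit in different subjects subgroups".

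Several listed variables are ordered:

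- Section 9.3.2 has tolerability by investigator on four verbal grades, and "global assessment of tolerability by subjects: very good, good, moderate and poor".
- Section 9.3.2 also lists severity of adverse events. Section 11.2.1 defines it: "Severity of adverse events should be graded as follows", followed by mild, moderate and severe.
- Section 9.3.3 has a 0 to 4 improvement score by subjects and, for investigators, "global assessment of improvement by investigators score (0 to 5 scale: 0 = worse; 1 = no appreciable improvement", continuing up to 5 for complete resolution.

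**The concern.** Pearson's chi-square test gives the same statistic in whatever order the grades are listed. For four grades in two groups it spreads its sensitivity over three degrees of freedom, although the difference one would usually look for, that one group tolerates the product worse, runs in a single direction. A rank test puts its one degree of freedom on that direction.

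At stake is how well the comparisons of tolerability between indications can show a consistent shift. The effect measure matters too. A chi-square p-value comes with no single summary of how much worse one group did, whereas an ordinal analysis supplies one.

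**Working it through.** **1. Which variables fall under the chi-square rule?**

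- *Tolerability* (four verbal grades) is categorical on any ordinary reading, so the rule applies.
- *Severity* (three verbal grades) is also categorical, but section 11.2 has it assessed for each adverse event. A test on subjects needs a per-subject summary such as the worst grade, and the number of subjects with an event is unknown.
- *Improvement* is defined as a numeric score. It could be treated as continuous and go to the t-test or Wilcoxon. The text does not settle this.

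**2. Degrees of freedom.** Chi-square uses (groups − 1) × (grades − 1).

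- Two groups, tolerability: 1 × 3 = 3, against 1 for Wilcoxon.
- Two groups, severity: 1 × 2 = 2.
- Five indications (section 9.2.1), tolerability: 4 × 3 = 12, against 4 for Kruskal-Wallis.

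The independent-group tests named for continuous data are two-sample tests. Among the named group tests, only chi-square extends to five groups.

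**3. Analytic size of the loss.** The protocol gives no power figure to reproduce. Suppose the whole difference lies in the ordered direction, so that both tests share the noncentrality λ = (z₀.₉₇₅ + z_power)².

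- Ordered test at 80% power: λ = (1.960 + 0.842)² = 7.85. Chi-square on 3 df then has 64.5% power, a loss of 15.5 points. On 2 df it has 70.9%, a loss of 9.1 points.
- Ordered test at 99% power: λ = 18.37. Chi-square on 3 df has 96.3%, a loss of 2.7 points.
- The largest loss at any effect size is 17.0 points for four grades and 10.5 for three.

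**4. Simulation for four grades.** Inputs from the protocol: 500 subjects, five indications, two-sided 5%. Assumed: equal splits (500/5 = 100 per group, or 500/2 = 250), the grade distributions, and a proportional-odds shift toward worse ratings. For example, 60/30/7/3% has cumulative proportions 0.60, 0.90 and 0.97, that is odds 1.5, 9 and 32.3. Halving them for odds ratio 2 gives 0.75, 4.5 and 16.2, and so 42.9/39.0/12.4/5.8%. Each row has 20,000 runs.

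| Reference grades, % | Per group | Odds ratio | Chi-square | Wilcoxon | Gap, points | Tables with an expected count below 5 |
|---|---|---|---|---|---|---|
| 60/30/7/3 | 100 | 2 | 55.2% | 72.8% | 17.6 | 61% |
| 60/30/7/3 | 250 | 1.5 | 47.1% | 64.5% | 17.4 | 1% |
| 75/20/4/1 | 100 | 2 | 45.1% | 63.3% | 18.2 | 96% |
| 75/20/4/1 | 250 | 1.5 | 37.5% | 54.2% | 16.7 | 90% |
| 45/35/15/5 | 100 | 2 | 59.2% | 75.7% | 16.5 | 8% |
| 45/35/15/5 | 250 | 1.5 | 52.7% | 69.4% | 16.7 | 0% |

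Some gaps exceed 17.0 because chi-square is slightly conservative in sparse tables.

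**5. Where the gap closes or reverses.**

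- 60/30/7/3, 100 per group, odds ratio 1.3: 10.3% vs 15.4%, a gap of 5 points.
- 60/30/7/3, 250 per group, odds ratio 2.5: 99.8% vs 100.0%.
- Not one-directional, 250 per group, 25/25/25/25 vs 33/17/17/33: chi-square 88%, Wilcoxon 5%.

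**6. Five indications.** With four groups of 100 at 60/30/7/3 and one at odds ratio 2, chi-square has 53% power and Kruskal-Wallis 73%. An expected count below 5 occurs in 94% of these tables.

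**7. Type I error.** With equal groups and no difference, chi-square rejected in 3.5% to 4.9% of runs and Wilcoxon in 4.8% to 5.1%.

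**The case against.** The strongest reply is that this belongs in the SAP. Section 9.7 calls itself a specification for the SAP, says that analysis will follow the nature of the data, and allows documented departures. Section 9.7.1 calls the analysis descriptive, and section 9.5 says that no power calculation was attempted. On this view the list in 9.7.1 is generic, and an ordinal test can be chosen later.

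Part of this stands. There is no power target to miss, by indication only a stratified analysis is described, and the primary objectives (frequency of adverse drug reactions, proportion with adverse renal effects) are not ordered outcomes. But the general remark about the nature of the data is followed by a specific rule. Section 9.7.1 also says that comparative analysis will be done. A rank test on tolerability would therefore be a departure from the protocol that has to be documented, when it could be the stated method.

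The non-monotone example is a fair objection to replacing chi-square without further thought. It is the reason to keep the full frequency tables.

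Four stronger readings are tempting, and the protocol does not support them:

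- *Every categorical outcome goes to chi-square.* McNemar's test and logistic regression are named too.
- *The comparisons by renal risk are weakened.* Those strata (prior renal impairment, nephrotoxic medicines) apply to the adjudicated renal event, which is yes or no.
- *The loss reaches about 26 points.* Gaps of that size arise only with the improvement scores, which may be analysed as continuous.
- *Sparse cells make the chi-square result unreliable.* With equal groups its type I error stayed at or below 5%, and section 9.7 allows sparse analyses to be dropped.

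**Conclusion.** The point holds in a limited form. Section 9.7.1 assigns the four-grade tolerability ratings to a test that ignores their order, and would do the same to worst severity per subject if that were compared. For the improvement scores the text is ambiguous rather than wrong.

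The gap of about 16 to 18 points for four grades is illustrative. It rests on an assumed proportional-odds shift, assumed grade distributions, equal groups of 100 or 250, and odds ratios of 2 or 1.5. It falls toward zero for very small or very large effects and reverses for differences that are not one-directional. The severity grades would lose less (at most 10.5 points analytically), on an unknown number of subjects.

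A reader might infer that a non-significant chi-square will be reported as similar tolerability across indications. Nothing in the protocol says so. The analyses are exploratory, and this is a refinement worth making, not a flaw that threatens the study.

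**What to change.** In section 9.7.1, limit the chi-square test, in exact form when tables are sparse, to binary and unordered variables. Add that ordered grades are compared by the Wilcoxon rank-sum test for two groups or Kruskal-Wallis for the five indications, or by a proportional-odds model. Ordered grades here means tolerability, the 0 to 4 and 0 to 5 improvement scores, and worst severity per subject. Report an effect estimate with its 95% CI, such as a common odds ratio or a probability of superiority. Define the per-subject severity summary, because a rank test on individual events would ignore that one subject can have several. Keep the full frequency tables by indication.

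The cost is one or two sentences in the protocol, carried into the SAP, with no further data or patient burden. The downside is less sensitivity to patterns that are not one-directional, which the frequency tables would still show.

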9.2.4. Study visits

It is planned to observe each subject for one cycle of treatment with Polyoxidonium. In accordance with the Summary of Product Characteristics (SmPC), the treatment course consists of 5-10 injections depending on the disease. Thus, study duration for individual subject will take 7-23 days. There will be 5-10 study visits coinciding with routine visits to receive Polyoxidonium injections at the health care centre (see Study flow chart in Table 1). If any visit (scheduled or unscheduled) occurs within 30 days after the last injection of Polyoxidonium as a part of routine practice, information on adverse events will be recorded.

Table 1. Study flow chart

Study procedures	Study visits			
	First injection	Interim visits (3 to 8, depending on indication)	Last injection	Follow-up*
Day	Day 1		Day 7 to 23	
Inclusion/exclusion criteria	X			
Informed consent	X			
Demographic data	X			
Height and weight	X			
Medical history	X			
Physical examination**	X	X	X	
Information about relevant infection, allergic condition, etc.	X	X	X	
Vital signs (blood pressure, heart rate, body temperature)**	X	X	X	
Laboratory tests**	X	X	X	
ECG**	X	X	X	
Other diagnostic procedures**	X	X	X	
Polyoxidonium administration	X	X	X	
Concomitant medications	X	X	X	
Adverse events	X	X	X	X
Investigator's and subject's assessment of tolerability and improvement			X	

*any visit (scheduled or unscheduled) which occurs within 30 days after the last injection of Polyoxidonium as a part of routine clinical practice

**if undertaken as a part of routine clinical practice. Results of laboratory tests, ECG examinations and other diagnostic procedures should be recorded only if performed within 3 days before subject's enrolment and (or) during the study period.

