9.2.6. Dosage and method of administration of Polyoxidonium

Subjects will be treated with Polyoxidonium in accordance with the posology and method of administration as per current version of SmPC approved by State Institute for Drug Control of Slovakia. Depending on the disease, Polyoxidonium treatment regimen consists of 5-10 injections:

- Acute inflammatory diseases, complicated forms of allergic diseases: 6 mg daily for 3 days, then on alternate days, 5-10 injections totally.
- Chronic inflammatory diseases: five 6 mg injections every other day, then twice weekly, 10 injections totally.
- Urogenital inflammatory diseases: 6 mg every other day, 10 injections totally.
- Chronic recurrent herpes simplex: 6 mg every other day, 10 injections totally.
- Allergic diseases: 6 mg daily for 2 days, then on alternate days, 5 injections totally.

Polyoxidonium is given intramuscularly as a slow injection (15-20 sec) into the deltoid muscle of the upper limb or outer upper quadrant of the thigh.

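### Section 9.7.1 names the Student (equal-variance) t-test for two independent samples; Welch's version is a safer default for subgroups of uncontrolled size (minor)

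*Protocol*

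**What the plan says.** Section 9.7.1 of the protocol states: "Parametric Student t-test or nonparametric Wilcoxon rank sum test will be used for comparison of continuous data between two independent samples". All tests are to be read at the two-sided 5% level. The section names no unequal-variance form, gives no rule for choosing between the two tests, and does not say which groups form the two samples.

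The same section describes the aim in two ways. First, "no statistical hypothesis testing is intended. Statistical analysis will be merely descriptive in nature"; shortly afterwards, "Comparative statistical analysis will be also performed". It then names three groupings. Prior renal impairment and nephrotoxic co-medication are tied to the renal event, which is binary. The third is indication: "Stratified analysis by indication will be performed to investigate safety profile and clinical benefit in different subjects subgroups".

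Section 9.7 presents this text as the specification from which the SAP is to be written, and requires any departure to be identified and documented there. Section 9.5 expects 500 subjects. Section 9.1 describes an uncontrolled design, section 9.2.1 lists five indication categories, and sections 9.2 and 9.9 describe consecutive enrolment of eligible patients, with no quota by indication.

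**The concern.** The equal-variance t-test holds its level under unequal spread only when the two groups are of about the same size. With no randomised arms and no quotas, nothing here keeps subgroup sizes equal. Indication is the one named grouping that the plan links to clinical benefit, where the continuous outcomes mainly lie, so it is the likeliest place for a two-sample test.

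Unequal spread is plausible for some of these outcomes. Course length depends on the disease: compare "6 mg daily for 2 days, then on alternate days, 5 injections totally" for allergic disease with "five 6 mg injections every other day, then twice weekly, 10 injections totally" for chronic inflammatory disease in section 9.2.6. Section 9.2.4 says: "Thus, study duration for individual subject will take 7-23 days". Counts of days with fever or symptoms during observation could well vary more in the longer courses.

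If the smaller group has the larger spread, differences between subgroups would be called significant too often when the means are equal. If the larger group has it, real differences would be missed. The confidence interval for the mean difference would be too narrow or too wide in the same way.

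**Working it through.** **Inputs from the protocol.** Two-sided level 0.05 (9.7.1); N = 500 (9.5).

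**Assumed inputs.** The protocol gives no standard deviations (SDs) and no split by subgroup. The check takes SD ratios of 1, 1.5 and 2, splits of 500 from 1:1 to 1:4, and equal true means.

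**Formula.** In large samples the pooled test estimates the variance of the mean difference as s1²/n2 + s2²/n1. The true variance is s1²/n1 + s2²/n2. With R the first divided by the second, the true level is 2 × [1 − Φ(1.96 × √R)].

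**Reproducing the plan's figure.** With equal SDs, R = 1 and the level is 5.0%, as stated.

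**SD ratio 1.5, split 125:375.**
- Larger SD in the smaller group: R = (2.25/375 + 1/125) / (2.25/125 + 1/375) = 0.01400/0.02067 = 0.677. 1.96 × √0.677 = 1.613, so the level is 10.7%.
- Larger SD in the larger group: R = 0.02067/0.01400 = 1.476. 1.96 × √1.476 = 2.381, so the level is 1.7%.

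**SD ratio 2, split 125:375.**
- Larger SD in the smaller group: R = (4/375 + 1/125) / (4/125 + 1/375) = 0.01867/0.03467 = 0.538. 1.96 × √0.538 = 1.438, so the level is 15.0%.
- Larger SD in the larger group: R = 1.857. 1.96 × √1.857 = 2.671, so the level is 0.76%.

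**Range over splits** (larger SD in the smaller group / in the larger group):

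| Split | SD ratio 1 | SD ratio 1.5 | SD ratio 2 |
|---|---|---|---|
| 250:250 | 5.0% | 5.0% | 5.0% |
| 200:300 | 5.0% | 7.0% / 3.4% | 8.2% / 2.7% |
| 167:333 | 5.0% | 8.5% / 2.6% | 10.9% / 1.7% |
| 125:375 | 5.0% | 10.7% / 1.7% | 15.0% / 0.76% |
| 100:400 | 5.0% | 12.1% / 1.3% | 17.9% / 0.43% |

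The level depends on the ratio of the sizes, not their total: 50:150 gives the same values as 125:375.

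**Interval.** Coverage of the nominal 95% pooled interval is one minus the level. At 125:375 it is about 89% or 98% at SD ratio 1.5, and 85% or 99% at ratio 2.

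**Simulation check** (6,000 runs per setting, normal data, equal means, 125:375). The pooled test gave 10.5% / 1.7% at ratio 1.5 and 14.7% / 0.65% at ratio 2, in line with the formula. The rank sum test gave 7.4% / 3.0% and 10.0% / 1.8%, so it is also affected, but less. Welch's test stayed between 4.7% and 5.3% in every setting run.

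**Cost of Welch when variances are equal.** At 125:375 its degrees of freedom are (1/125 + 1/375)² / [(1/125)²/124 + (1/375)²/374] ≈ 213, against 498 for the pooled test. Using 1.96 + (1.96³ + 1.96)/(4 × df), the critical value moves from about 1.965 to 1.971.

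**The case against.** The strongest reply is that this is SAP detail with little resting on it. The protocol calls its analysis descriptive, the primary objectives are frequencies and proportions, and no stated decision depends on a p-value for a continuous outcome. The SAP may depart from section 9.7.1 if it documents the change. This stands as to weight and keeps the point minor. It does not remove the point: the protocol does not leave the choice open but names a test, and a SAP that follows its specification inherits it.

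A second reply is that the protocol never assigns the two-sample test to indications. That is correct. Stratified analysis can mean analysis within each stratum, and five categories do not suggest a two-sample test. Indication is only an example here; the argument applies to any two subgroups of unequal size. The reading of the Student test as the pooled form is its ordinary meaning, not the protocol's wording.

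A reader might infer stronger claims, which the documents do not support:

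- **That the 5% level becomes about 0.2% or over 20%.** For the t-test this needs an SD ratio as large as 23/7 = 3.29 with a 125:375 split (20.8% or 0.23%), or a more extreme split. It treats SD as proportional to observation length, which the protocol does not state. It does not apply to the rank sum test, which gave 12.7% or 1.75% in that setting.
- **That SDs can be derived by spreading day counts evenly over the window.** This assumption also makes the means differ, at about half the window. For an 8-day and a 19-day window the means are 4 and 9.5 days and the SDs 2.3 and 5.5. With 50 short-course and 150 long-course subjects the pooled standard error is √(5.5²/50 + 2.3²/150) = 0.80, so the difference of 5.5 days is about 7 standard errors. False-positive or power figures that presume equal or nearly equal means do not follow from it.
- **That all continuous outcomes are affected.** The documents give no reason for unequal spread in white cell counts or global ratings, and duration of primary treatment is not shown to be confined to the injection window.
- **That ten-injection courses all end between Day 19 and Day 23.** Counted from section 9.2.6 they end on Day 17, Day 19 or about Day 26. The last lies outside the 7 to 23 days of section 9.2.4. The two sections need reconciling, but nothing in this check uses those days.

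**Conclusion.** The point holds in a limited form. Section 9.7.1 fixes an equal-variance test for comparisons between subgroups whose sizes the design does not control. At a 125:375 split the true level would be about 11% or 1.7% at an SD ratio of 1.5, and about 15% or 0.8% at a ratio of 2. These figures rest on assumed SDs and splits. They shrink towards 5% as the groups become equal in size or in spread, and vanish if either is equal. They concern the t-test only.

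Severity is minor. The tests support secondary, descriptive analyses, and no primary conclusion depends on them.

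**What to change.** In section 9.7.1, for two independent samples, replace the Student t-test with Welch's unequal-variance t-test as the default parametric test, and report its confidence interval for the mean difference. The paired test for dependent samples needs no change.

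The cost is one line of wording, carried into the SAP. The loss of power if variances are equal is negligible at these sizes.

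The change corrects the error rate and the interval only. If day counts are compared between subgroups observed for different lengths of time, the means can differ because of the window alone, and Welch's test would not correct that.
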